#### 4. INTRODUCTION

##### a. BACKGROUND

Breast milk is the first and best source of nutrition for babies that is natural. Breast milk contains a variety of nutrients needed in the growth and development process of the baby. Breast milk also plays a role in enhancing sensory and cognitive development, and protects infants against infectious diseases.

The World Health Organization (WHO) recommends exclusive breastfeeding for the first six months of infancy to achieve optimal growth and development (Kramer and Kakuma, 2012). Exclusive breastfeeding has been shown to reduce infant mortality from common diseases such as diarrhea and pneumonia. In addition, exclusive breastfeeding can help accelerate healing in sick infants (Kramer et al., 2001). Breastfeeding also affects maternal health and well-being, such as reducing the risk of ovarian cancer and breast cancer, and increasing family and national resources.

Various attempts have been done since ancient times to deal with the problem of low breastmilk production in breastfeeding mothers. Pharmacological and non-pharmacological interventions is given to increase breastmilk production. Prescribing drugs that increase breastmilk supply, otherwise known as galactagogues, needs to be considered since breastmilk is important for a baby's health. A modern drug that is indicated as a galactagogue among others is domperidone and metoclopramide. Domperidone is a dopamine D2 receptor antagonist. Metoclopramide falls under the same drug class as domperidone that works as a dopamine D2 receptor antagonist. However, in terms of its traits, domperidone is less permeable than metoclopramide, less soluble in water, and has a higher molecular weight, which in turn causes less extrapyramidal effects in comparison to metoclopramide. By looking at the traits and characteristics, domperidone is more recommended than metoclopramide.

Several traditional herbs have been used and is well known since a long time ago by Indonesian people to increase the production of breastmilk, such as Katuk leaves (*Sauvopis*

*androgynous Folium*), Fenugreek (*Trigonella foenum-graceum*), and Moringa leaves (*Moringa oleifera Folium*). These plants have been scientifically proven through preclinical and even clinical research. However, not many have been further developed as phytopharmaceuticals that can be used in formal health services.

In previous research, ASI MOMMY® capsules have been successfully produced in accordance to the traditional method of making good herbal drugs, with each capsule containing extracts of Katuk leaf (300 mg), Fenugreek (150 mg), and Moringa leaf (50 mg). This formulation has gone through pharmacodynamic activity test, and acute and subacute toxicity test. Research has shown that ASI MOMMY® works actively as a galactogogue and is not toxic, therefore it is safe to be given to humans (unpublished),

No research has been done to test the benefits of ASI MOMMY® in increasing breastmilk production. Therefore, this research is a clinical trial that intends to see the benefits of ASI MOMMY® for increasing breastmilk production in postpartum women. This research is a part of the previous main research that is still ongoing to this day which aims to develop the formulation of ASI MOMMY® as a phytopharmaceutical.

## 5. PURPOSE

The aim of this research is to study the benefits of ASI MOMMY® for increasing production of breastmilk in postpartum women.

## 6. BENEFIT

Benefits of conducting this research are as follows:

### a. Theoretical Benefit

This research is hoped to be beneficial for becoming the basis of research and development in knowledge regarding breastmilk enhancing drugs for postpartum women.

### b. Academic Benefit (Scientific)

This research is hoped to give contribution to the field of Pharmacology and Medicine, for studying the benefits of ASI MOMMY® traditional medicine formulation in increasing the production of breastmilk in postpartum women by looking at the increase in babies' body weight. The data obtained is hoped to provide the basic data for developing future research studies, because there is still a lack of research about phytopharmaceuticals concerning breastmilk in Indonesia.

### c. Health Services

Data collected from this research will help citizens in obtaining herbal preparations that is safe and effective, and backed up by scientific evidence. Aside from that, it will also help the government in improving programs concerning exclusively breastfeeding women.

## 7. INFORMATIONAL RELATED TO THE THERAPHY

ASIMOMMY® is one product produced by PT Swayasa Perkasa Yogyakarta Indonesia which traditionally can increase the production of breastmilk. Instructions for product storage, ingredients and benefits of ASIMOMMY® are enclosed in the leaflet.

ASIMOMMY® contains several different natural components such as *Sauropi folium* extract (Katuk leaf), *Foenigraeci semen* extract (Fenugreek), and *Moringae folium* extract (Moringa leaf). Components in ASIMOMMY® ingredients is beneficial in enhancing breastmilk because it is rich in nutrition that is useful in the growth and development of babies.

The recommended direction for storage is to keep it in a place with temperature below 30 degrees Celsius, in a dry place away from sunlight exposure.

## 8. STUDY DESIGN

### a. Overview of The Study Design

This research is a pilot study, single blind, randomized controlled trial. Subjects are allocated to three groups with a randomized list. The three treatment groups are the intervention group, positive control group, and negative control group. The intervention group is the group of patients that receive ASI MOMMY®, the positive control group are patients that receive domperidone, and the negative control group is the placebo group.

### b. Duration of The Study and Visit Schedule

In the beginning of this reasearch, on the third day postpartum, the babies' weights are measured before starting the intervention. There are 3 treatment groups, a group that is given domperidone, ASI MOMMY®, and placebo. The information about which drug intervention given is hidden, where both the researcher and subjects do not know which type of treatment they are receiving. Domperidone is given in the form of tablet with a dosage of 10 mg orally, taken every 8 hours, three times a day at 06.00, 14.00, and 22.00 West Indonesia time for a duration of 7 days. ASI MOMMY® and placebo capsules is taken once a day at nighttime, as much as 2 capsules for a duration of 7 days. The capsule is given to the subjects that have been randomised. All subjects will receive all the drugs in the first day to be taken for the next 7 days. The drug given is not known to the researcher nor the subject. Aside from that, the research asistant and family of the subjects helps monitor the subjects regarding the regularity and adherence of taking the drugs.

## 9. STUDY POPULATION

### a. Subject Recruitment

Data collection is done by healthcare providers on duty. Data collection is conducted starting from July 2022 until December 2022 by finding information about mothers in labor from Jfestis and Tegalrejo public health centers. Women in

puerperium who meet the inclusion and exclusion criteria are gathered in the research until the number of samples needed is fulfilled.

The researcher explains the research intent, method, and procedure that will be done to the mother. Then the mother is allowed to sign the informed consent form if they agree to become a research subject. The research subjects are given lactation counseling. Next, the research subjects are randomized by the researcher using the random number table with each group containing 15 subjects. The researcher will allocate each group with one type of treatment, that is drug A, drug B, and drug C, then randomization is conducted. The list of randomizations is kept by the researcher.

b. Populasi

The subject population in this research are postpartum women from Tegalrejo Public Health Center and Jetis Public Health Center in Yogyakarta who plan to breastfeed their baby.

c. Inclusion Criteria

- a. Gestational age 37-40 weeks at labor
- b. Giving birth vaginally
- c. Normal body mass index (BMI 18.5-24.9 kg/m^2)
- d. Does not consume drugs or supplements to enhance breastmilk
- e. Healthy women with normal nipple condition (protrudes)
- f. Condition of baby is health with good suction reflex
- g. Baby currently only consumes breastmilk

d. Exclusion Criteria

- a. Allergy towards ASI MOMMY® and Domperidone
- b. Women who consumes drugs that influences the effects of domperidone (such as antacids, cimetidine, ranitidine, famotidine, and nizatidine) or drugs that interacts with domperidone (such as haloperidol, lithium).
- c. Women who are in sick condition and needs in-hospital treatment
- d. Women with HIV AIDS, heart problems, mastitis, and a history of breast surgery
- e. Underweight, overweight, and obese women
- f. Twin pregnancies
- g. Babies born with a congenital disease that affects the breastfeeding process
- h. Babies and mothers who do not follow the regimen from start to finish (seventh day of intervention)

e. Number of CTP Sites

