## 10. CLINICAL TRIAL PROCEDURE

a. Recruitment and Enrollment

The research team will fill the recruiter information log sheet. All subject candidates will receive starting information and disclose their willingness to participate in the clinical trial and consent to give information about their phone number and home address.

b. Recruitment Plan

Research subject candidates are recruited until the amount of subjects fulfill the minimal sample amount that has been determined by the research team.

c. Initial Subject Screening

During initial screening the screening form will be filled, the researcher will fill the screening log, and if the subject candidate fulfills the inclusion and exclusion criteria of the research, they will be given a subject ID number by the research team.

d. Informed Consent Procedure

Research subjects will be given starting information and be given the opportunity to ask questions if they still have questions regarding the research. After it is made sure that the research subjects have understood and received information about the research, the doctor or midwife on site will ask for the subject's signature for willingness to participate in every step of the research.

e. Baseline Assessment

This study includes interviews related to the demographic data of the subjects.

f. Randomization

Randomization using random numbers that is obtained from the random numbers table. The randomized list is placed inside a non-transparent, sealed envelope and is given serial numbers according to the number of subjects. The envelopes are held by one of the researchers and kept in the Center. Every subject that fulfills the criteria to participate in the research will be reported to the Center and Research Site, and an envelope is taken according to the serial numbers.

g. Treatment

i. Subject Discontinuation Criteria

In this research, the criteria for sample drop out includes subjects/babies who are sick and cannot continue participating in the research, babies who drink baby formula during the intervention, and subjects who consecutively skips consuming the capsules.

Termination of the intervention is done if the subject experiences side effects or serious adverse effects and will be examined by the research doctor for further observation and will receive treatment according to the research flow and placed in the intervention termination form.

ii. Treatment Discontinuation

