Drug administration will end when the patient has completed the research process or the subject is placed under the drop out criteria.

iii. Replacement of Subject

Replacement of research subject is done if the number of subjects that is needed in the research does not fulfill the minimum amount due to drop out or termination of intervention.

iv. Follow-up of Withdrawn Subject

Subjects who withdraw due to heavy allergic reactions will receive monitoring by the research doctor and if the subject withdraws due to other dropout factors then the subject is required to give the product back to the research team.

h. Follow Up

Follow up of research subjects will be done by research assistants by giving periodical reminders of when to take the drug through WhatsApp broadcasting that is given to the research assistants by the subjects.

i. Blinding

i. Type(s) of Blinding

The type of blinding done is single blind, where the researcher knows the type of capsule product given to each respondent, however, the respondent and research assistants or operator who administers the product does not know which type or product is given to the respondent

ii. Maintenance of Blinding

To maintain the blinding, the list of randomization is only kept and known by the researcher.

iii. Breaking the Blinding

The list of randomization will be opened at the end of the research when all the research process is finished.

j. Preventions of the Subject Dropout

To prevent dropout of subjects, the research assistants will periodically remind the subjects when to take the capsules and schedule for next visit.

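### One role recruits, screens, randomises and knows the randomisation list, and nothing bars the list holder from recruiting, so the sealed envelopes do not secure concealment from that role

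*Protocol*

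**What the plan says.** **Recruitment and randomisation (Protocol 9.a).** "The researcher explains the research intent, method, and procedure that will be done to the mother". After consent and lactation counselling, "the research subjects are randomized by the researcher using the random number table with each group containing 15 subjects". On the treatment code: "The researcher will allocate each group with one type of treatment, that is drug A, drug B, and drug C". On custody: "The list of randomizations is kept by the researcher".

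**Screening (10.c).** In the same step in which eligibility is established, "the researcher will fill the screening log".

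**Concealment device (10.f).** The list goes into opaque, sealed, serially numbered envelopes. "The envelopes are held by one of the researchers and kept in the Center". A subject who meets the criteria is reported to the Center and the site, and an envelope is then taken in serial order.

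**Knowledge of the list and product (10.i.i and 10.i.ii).** The design is single blind, "where the researcher knows the type of capsule product given to each respondent", while respondents and the assistants or operators who hand out the product are blind. To maintain this, "the list of randomization is only kept and known by the researcher".

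**Contrary statements.** Section 8.b says twice that the researcher does not know the treatment. Section 10.i.iii says the list is opened only when the research is finished.

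**Other people involved.** Section 9.a gives data collection to the healthcare providers on duty, 10.c has the research team issue the subject ID, and 10.d has the doctor or midwife on site take the signature.

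**The concern.** Opaque, numbered envelopes exist so that whoever brings a subject into the trial cannot foresee the next arm. They do nothing against a person who knows the list they were filled from. Here the role that recruits also knows the list and sets the A/B/C key, so the letter code hides nothing from it either.

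This is about selection before assignment. It is a separate question from who is masked afterwards: a single-blind or even open-label trial can still conceal allocation, and the choice of envelopes shows that this protocol means to.

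Two features raise the stakes. Several entry criteria in 9.c call for judgement (a healthy mother, nipple condition, the baby's suction), and these plausibly bear on the outcome in the synopsis, the baby's weight gain over 7 days. Each arm also has only 15 babies, so a few selectively included or excluded pairs could move an arm mean. Later masking or analysis cannot reliably undo that kind of selection.

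**Working it through.** The protocol states no figure on this point, so the check is mainly a comparison of who does what.

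**1. Tasks by role**

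| Task | Who | Section |
|---|---|---|
| Explains the study to the mother | the researcher | 9.a |
| Fills the screening log | the researcher | 10.c |
| Fills the screening form | not stated | 10.c |
| Takes the consent signature | doctor or midwife on site | 10.d |
| Issues the subject ID | research team | 10.c |
| Sets which product is A, B or C | the researcher | 9.a |
| Randomises | the researcher | 9.a |
| Keeps the list | the researcher | 9.a, 10.i.ii |
| Knows the list and each product | the researcher | 10.i.i, 10.i.ii |
| Holds the envelopes | one of the researchers, at the Center | 10.f |

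Explaining, logging, coding, randomising, keeping and knowing all fall to one role. No row or sentence says that whoever holds the list or envelopes stays out of recruitment or screening.

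**2. Does 10.f repair this?** In part. Eligibility is reported before the envelope is drawn, which protects against a recruiter who does not know the list. It gives no protection against one who does, because that person can foresee the arm before reporting anyone.

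**3. Do the contrary statements repair it?** No. Sections 8.b and 10.i.iii cannot both stand with 10.i.i and 10.i.ii. They show that the text is unsettled. They do not show that the list is hidden from the recruiter.

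**4. How foreseeable is the next allocation?** This is an illustration for a list with exactly 15 per arm (3 × 15 = 45), ignoring replacements.

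- List known: 45 of 45 (100%).
- Neither list nor past allocations known: 45 × 1/3 = 15 of 45 (33.3%).
- Only past allocations known, always guessing the arm with most places left. With a, b, c places left and n = a + b + c, the expected number of correct guesses is E(a,b,c) = max(a,b,c)/n + the sum over arms of (places left in arm / n) × E(with that arm reduced by 1), and E(0,0,0) = 0. This gives E(15,15,15) = 19.66, and 19.66/45 = 43.7%.

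**5. What could it do to an arm mean?** If m of 15 babies are steered and each differs by d in 7-day gain, the arm mean shifts by m × d / 15. Equal and opposite steering in the comparator doubles the between-arm shift. Taking d = 100 g as an assumption:

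| m | One arm steered | Both arms, opposite directions |
|---|---|---|
| 1 | 100/15 = 6.7 g | 13.3 g |
| 2 | 200/15 = 13.3 g | 26.7 g |
| 3 | 300/15 = 20.0 g | 40.0 g |

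All entries scale in proportion to d. Both m and d are assumed. The protocol gives no standard deviation or target difference for weight gain (14.b lists mean body weights and leaves S without a value), so there is no yardstick for these figures.

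**The case against.** The strongest reply is that a role is not a person. The researcher may be a label for several team members. Section 10.f speaks of one among several researchers holding the envelopes, and places them at the Center, away from the sites. If that person never recruits, concealment could work well in practice. This stands as a limit on the point: the text shows that separation is not stated, not that it is absent in practice.

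Other parts of the reply also stand:

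- A reader might infer that the list holder will be the one judging suction reflex or nipple condition. No section says so. Completing a log is record-keeping, and providers on duty, a doctor or a midwife are also involved.
- A reader might infer that mothers could be held back for a more favourable envelope. The start on day 3 postpartum leaves little room for that. Selective exclusion, or choosing the order among pairs eligible on the same day, remains possible.
- The gram figures show how the arithmetic behaves, not how likely or large a bias is.

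One part does not stand. The statements in 8.b and 10.i.iii that the researcher is unaware, or that the list stays closed, do not dispose of the point, because 10.i.i and 10.i.ii expressly say the opposite.

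**Conclusion.** The point holds as a defect in what the protocol fixes. It assigns recruiting tasks and knowledge of the list to one role, places no bar between them, and contradicts itself on whether that role knows the allocation. As written, the envelopes do not secure concealment from the researcher role.

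The stronger readings, that the next allocation is in fact exposed at every enrolment or that the ASI MOMMY comparison will be biased, are not supported. They require the person recruiting to be the person with the list, and the documents leave that open.

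On size, foreknowledge for anyone with the list is complete (45 of 45, against 15 of 45 expected by chance), assuming a fixed 15/15/15 list. The effect on weight gain is unknown. The ranges of about 7–20 g (one arm) and 13–40 g (two arms) are illustrative and rest wholly on the assumed 1–3 steered babies per arm and the assumed 100 g difference. The change is worth making because it is cheap and because selection cannot be put right after enrolment.

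**What to change.** - **Custody (9.a, 10.f, 10.i.ii).** State that the list, the A/B/C key and the envelopes are prepared and held by a team member, named by role, who takes no part in recruitment, screening, consent or weighing. Preferably this is not the biostatistics expert of 14.f. That expert carries out the entire data analysis, and giving the analyst the list would trade one exposure for another.
- **Release (10.f).** State that the Center releases the next envelope only after eligibility, consent, subject ID and baseline weight are recorded. Check the Section 3 table against this, since it places randomisation in the screening/baseline column.
- **Deletion.** Remove the statements that the recruiting researcher keeps or knows the list.
- **Reconciliation.** Bring 8.b, 10.i.i, 10.i.ii and 10.i.iii to a single statement of who knows the list and the product, and from when.

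**Cost.** Protocol wording, one task moved to another team member, and a stricter form of the report to the Center that 10.f already requires. The small downside is that an envelope must wait until the four items are recorded.

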## 2. STUDY SYNOPSIS AND SCHEMA

## Study Synopsis

[figure not shown]
Title	Efficacy of ASIMOMMY® Compared to Domperidone and Placebo in Increasing Breastfeeding: Randomized Single-Blind Controlled Trial in Indonesia.
Purpose	Assessing the efficacy of ASIMOMMY® in increasing breast milk production in postpartum mothers.
Hypothesis	ASI MOMMY® increases milk production in postpartum mothers.
Methodology	
Study Design	Randomized Control Trial (RCT) .
Study Time	October 2022 until March 2022.
Study Location	Tegalrejo and Jetis Primary Health Care, Yogyakarta.
Study Product	
Treatment group	ASI MOMMY®.
Control group:	Domperidone and placebo.
Subject Criteria:	
Inclusion Criteria:	
 
Mothers 20-35 years old.
 
Gestational age at delivery 37-40 weeks.
 
Vaginal delivery.
 
Normal body mass index (BMI 18.5-24.9 kg/m^2).
 
Not taking drugs or breast milk enhancement supplements.
 
Healthy mother's condition with normal nipples (protruding).
 
Healthy baby condition with good suction reflex.
 
The baby consumes only breast milk.
 

Exclusion criteria:	
 
Allergy to ASI MOMMY® and Domperidone.
 
The mother is taking medications that affect the effects of domperidone (such as antacids, cimetidine, ranitidine, famotidine and nizatidine) or medications that interact with domperidone (such as haloperidol, lithium).
 
The mother is in a state of illness requiring hospitalization.
 
Mother has HIV AIDS, heart problems, mastitis, and had undergone breast surgery.
 
Underweight, overweight and obese mothers.
 
Giving birth to twins.
 
The baby has a congenital defect that affects the suctioning process of breast milk
 

	
 
• Infants and mothers who did not participate in the treatment until completion (day 7 of the intervention).
 

Sampel size	The sample size was 15 subjects per group. The total sample size was 45 subjects.
Subject Allocation Method	Randomization with a randomization list.

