### 14. STATISTICAL ANALYSIS

a. General Design

The method used in this research is a single blind, Randomized Control Trial (RCT). The benchmark of this study is the measurement of the babies' weight before and after the intervention therapy that is given (the research product).

i. Hypothesis

**H0:** The traditional drug preparation ASIMOMMY® does not increase breastmilk production in postpartum women.

**H1:** The traditional drug preparation ASIMOMMY® increases breastmilk production in postpartum women.

ii. Output (*Endpoint*)

The output expected is that ASI MOMMY® is able to increase the production of breastmilk which in turn increases the weight of the baby after the mother receives the intervention.

b. Rationale for Sample Size and Statistical Power

Sample size is calculated using sample size formula for hypothesis testing on the average of more than two groups, unpaired numeric comparative in one measurement, are as follows (Dahlan, 2016):

$$z_{\beta} = \frac{\sqrt{v_2(2[v_1+\delta^2]^2-[v_1+2\delta^2])} - \sqrt{v_1(v_1 + \delta^2)(2v_2 - 1)F}}{\sqrt{v_1}(v_1 + \delta^2)F + v_2(v_1 + \delta^2)}$$

Information:

$n$  = number of subjects in one group

$Z_{\beta}$  = beta standard value 20 % which is 0,84

$V_1$  = degree of freedom from the number of =  $k-1$ .  $V_1 = 3-1 = 2$

$V_2$  = degree of freedom from the number of groups  $k$  ( $n-1$ ).  $V_2 = 3(n-1)$

$K$  = number of groups = 3

$$\delta^2 = \frac{n \sum (x_i - \bar{x})^2}{s^2}$$

$X_i$  = average of baby body weight in a group

$X_1$  = average of baby body weight in the domperidone and placebo group which is 3426,6 (Amri *et al.*, 2020)

$X_2$  = average of baby body weight in the placebo group which is 3221,1 (Amri *et al.*, 2020)

$X_3$  = average of three groups is 3000

$X$  = overall average (3 group)

$S$  = combined standard deviationn

$F$  = Anova table value as function of type 1,  $V_1, V_2$

Alpha = type 1 error 0,05.

i. Projected Number of Site

Locations used in this study are two sites which are Jetis and Tegalrejo Public Health Centers in Yogyakarta.

ii. Projected Number of Participant per site

Total number of subjects in one place is around 22 or 23 subjects.

c. Statistical Methods for primary and Secondary Outcomes

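### Pairs who do not finish the 7-day regimen are excluded and replaced after randomisation, and no day-7 weight is required of them, so completers are compared rather than the randomised groups

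*Protocol*

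**What the plan says.** - **Exclusion.** Section 9.d, criterion h, excludes "Babies and mothers who do not follow the regimen from start to finish (seventh day of intervention". The Synopsis (section 2) repeats it: "Infants and mothers who did not participate in the treatment until completion (day 7 of the intervention".
- **Order of events.** Under section 10.f, a subject who meets the criteria is reported and the next numbered envelope is taken. Treatment then runs for 7 days, so criterion h can only be applied after allocation.
- **Drop-out.** Section 10.g.i states that "the criteria for sample drop out includes subjects/babies who are sick and cannot continue participating in the research", and adds "babies who drink baby formula during the intervention, and subjects who consecutively skips consuming the capsules". Side effects end the intervention.
- **Replacement.** Section 10.g.iii: "Replacement of research subject is done if the number of subjects that is needed in the research does not fulfill the minimum amount", whether through drop-out or termination. The Synopsis sets the number: "The sample size was 15 subjects per group. The total sample size was 45 subjects". No drop-out allowance is stated.
- **After withdrawal.** Section 10.g.iv provides medical monitoring after a severe allergic reaction. Otherwise, "if the subject withdraws due to other dropout factors then the subject is required to give the product back to the research team". It asks for no day-7 weight.
- **Outcome.** The Synopsis measures milk production by the baby's weight gain from day 0 to day 7. Section 14.a.ii expects the product to "increase the production of breastmilk which in turn increases the weight of the baby after the mother receives the intervention".

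**The concern.** An exclusion criterion should be decidable before allocation. This one removes pairs for what happens during treatment, and the replacement rule then fills their places with other pairs who finish.

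The reasons for leaving are unlikely to be neutral. A mother is more likely to turn to formula when her milk supply is low, and the protocol itself expects supply to drive the baby's weight. Removing formula users therefore removes likely treatment failures. Skipped capsules may also differ by arm, because domperidone is taken three times a day and the other two products once at night.

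Once pairs leave for such reasons, randomisation no longer protects the comparison. A real effect can shrink because the weaker results drop out mainly from the less effective arm. A false effect can appear if loss differs by arm for other reasons. Section 8.a calls the study a pilot, but section 14.a.i tests an efficacy hypothesis and section 18.e sends the results to the regulator.

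**Working it through.** The protocol states no drop-out rate and no bias figure, so there is no figure of its own to reproduce on this point. Taken from the protocol: 15 per group, 45 in total, three arms, alpha 0.05. Every rate and correlation below is an assumption.

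**1. How often replacement would arise.** This takes 45 as the minimum that section 10.g.iii refers to. With chance p of drop-out per pair, the chance of at least one loss is 1 − (1 − p)^45.
- p = 5%: 1 − 0.95^45 = 0.90
- p = 10%: 1 − 0.90^45 = 0.99
- p = 20%: 45 / 0.80 = about 56 pairs randomised to leave 45 finishers

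**2. Model for bias.** Weight gain Y is normal with SD 1 and mean 0 (control) or d (treated). A pair drops out when L = ρY + √(1 − ρ²)U falls below c, where U is independent standard normal noise. The cut-off c is set so that a given share of controls drops out. With a = c − ρ·mean and h = φ(a)/(1 − Φ(a)), the completers' mean is mean + ρh and their variance is 1 + ρ²(ah − h²).

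**3. True effect, same c in both arms.** Worked case with d = 0.5, ρ = 0.7 and 10% of controls lost: h is 0.195 in control and 0.111 in treated. The observed difference is 0.5 + 0.7 × (0.111 − 0.195) = 0.441. The standardised columns divide the difference by the SD of the analysed data.

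| ρ | True d | Raw, control loss 10/20/30% | Standardised, 10/20/30% |
|---|---|---|---|
| 0.3 | 0.5 | 0.488 / 0.482 / 0.478 | 0.494 / 0.491 / 0.489 |
| 0.7 | 0.5 | 0.441 / 0.410 / 0.388 | 0.470 / 0.453 / 0.440 |
| 0.7 | 1.0 | 0.904 / 0.846 / 0.801 | 0.952 / 0.920 / 0.895 |
| 1 (worst case) | 0.5 | 0.390 / 0.328 / 0.282 | 0.442 / 0.405 / 0.375 |

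At ρ = 0.7 and d = 0.5 the raw loss is 12% to 22%, or 6% to 12% in analysed SD units. At ρ = 0.3 the raw loss is 2% to 4%. At ρ = 1 (a sharp cut-off on gain) it is 22% to 44% raw, or 12% to 25% in analysed SD units.

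**4. No true effect, drop-out differing by arm, ρ = 0.7.** The bias is ρ × (difference in h), in favour of the arm that loses more.
- 20% v 5%: 0.7 × (0.350 − 0.109) = 0.169 SD
- 30% v 10%: 0.7 × (0.497 − 0.195) = 0.211 SD
- 20% v 20%: 0

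**5. False-positive rate.** Simulation with 200,000 trials and 15 finishers per arm. For the three-arm tests, both active arms have the lower drop-out rate.

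| ρ | Drop-out | Two-arm t test | Three-arm ANOVA | Bonferroni, ASI MOMMY v placebo |
|---|---|---|---|---|
| 0.7 | 20% v 5% | 7.7% | 7.3% | 2.9% |
| 0.7 | 30% v 10% | 9.6% | 8.9% | 3.8% |
| 0.7 | 20% in all arms | about 5% | about 5% | 1.7% |
| 0.3 | 20% v 5% | 5.5% | 5.4% | 1.9% |
| 0.3 | 30% v 10% | 5.7% | 5.5% | 1.9% |

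**The case against.** **Analysis sets belong in an analysis plan, which is not at hand.** Section 14 defines none, the Synopsis sets the day-7 weighing without exempting anyone, and section 10.g.iv is silent on weighing withdrawn subjects rather than forbidding it. This is fair as far as it goes. But eligibility, replacement and data collection are fixed in the protocol. An analysis plan cannot recover weights that were never taken, and analysing all randomised pairs would contradict criterion h.

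**The replacement minimum may be below 15 per group.** Section 10.b leaves it to the research team, and section 14.b gives no value for the SD, so 15 might contain a margin. This stands: that nearly any loss triggers replacement is an inference from a fixed target with no stated allowance.

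**Loss may be small.** Treatment lasts a week, babies take only breast milk at entry, mothers receive lactation counselling, and adherence is monitored with reminders. These measures should lower drop-out, and at a correlation of 0.3 the effect is slight. This limits the size, not the defect.

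**The planned tests are ANOVA with Bonferroni, not a two-arm t test.** The ANOVA inflation is nearly the same. The Bonferroni comparison stays under 5% in absolute terms but roughly doubles from its own baseline of 1.7%.

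**Formula adds weight that is not breast milk, so raw weights of supplemented babies mislead too.** This is correct, and it is the measurement reason for the formula rule. Removing and replacing those pairs does not solve that problem; it turns a measurement error into a selection.

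**Conclusion.** The concern holds. A post-randomisation event is used as an exclusion criterion in two places, the drop-outs are replaced, and nothing requires their day-7 weight. Followed as written, the comparison is between completers.

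Confidence in the reading of the text is high. The size is uncertain because the protocol gives no drop-out rate. Under a strong assumed link between drop-out and gain (0.7), a true 0.5 SD effect loses 12% to 22%, and unequal loss can produce a spurious difference of about 0.2 SD. Under a weak link (0.3) the loss is 2% to 4%. The direction is not fixed, and equal loss with no true effect gives no bias.

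It must nevertheless be fixed, pilot or not, because missing weights cannot be recovered once the trial has run and the remedy is cheap.

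**What to change.** 1. Delete criterion h from section 9.d and the matching bullet from the Synopsis.
2. Leave the rules for stopping study product as they are, but separate stopping product from leaving follow-up. State that every randomised baby is weighed at the existing day-7 visit unless consent is withdrawn.
3. State that all randomised pairs are analysed in their allocated group. Any subjects enrolled later to make up numbers are added to those already randomised and do not replace them.
4. Record formula use by arm and specify in advance how supplemented babies are handled. One option is a rank analysis placing them below exclusively breastfed babies. Whether that analysis is primary or supporting is for the investigators to choose.
5. Keep the completers analysis as supportive.

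The cost is protocol wording plus one weighing at an existing visit for each pair who stops early. Some records will still be incomplete, for example where a baby is too ill to attend, and the estimated effect may be smaller than among completers.
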